#### 8.7.4 Isometric dynamometry

Recovery of ankle dorsiflexion strength is essential in patients with foot drop. The use of dynamometry allows to document ankle dorsiflexion strength in an objective manner. Dynamometry has frequently been used to assess muscle strength in patients with foot drop (79-81). Won et al. (81) used a handheld dynamometer to assess ankle dorsiflexion strength in 52 patients with peroneal neuropathy (47 traumatic peroneal neuropathies and 3 idiopathic peroneal neuropathies). During the foot drop trial, results will be obtained and reported according to the same method.

Patients are asked to lay in a supine position, with the knees extended. The test pad of the dynamometer is placed on the dorsal head of the first metatarsal bone. The patient is instructed to perform ankle dorsiflexion with maximal muscle strength. The best of three attempts is registered. Ankle dorsiflexion is measured and reported for both ankles (in Newton). The ankle dorsiflexion strength ratio, defined as the ratio of ankle dorsiflexion strength in the affected ankle over ankle dorsiflexion strength in the healthy ankle will be calculated and reported in the eCRF. Training videos for the trial investigators will be made available, so that the inter-observer variability will be reduced to a strict minimum.

Based on the experience with isometric dynamometry throughout the FOOTDROP pilot study, following instructions are proposed to collect data in the most uniform way:

1. The ankle joint is placed in neutral position (90°). Aid the patient if necessary. Register the best of three attempts. If a patient is not able to generate any dorsiflexion strength, do not apply resistance, to avoid registering passive resistance.
2. The ankle joint is placed in 'natural position'. The natural position is defined as the position of the ankle joint in the sagittal plain when the patient is neither actively dorsiflexing or plantarflexing the ankle joint. Since the natural position is depending on muscle tone in both the dorsiflexion and plantarflexion muscles, this is patient (and time) dependent. Register the best of three attempts. If a patient is not able to generate any dorsiflexion strength, do not apply resistance, to avoid registering passive resistance.

3. Register normal strength in both positions at the contralateral healthy site in order to calculate the two relevant ankle dorsiflexion strength ratios (in neutral (90°) and natural position).

The use of isometric dynamometry is not considered standard of care. The treating physician will perform dynamometric measurements at 10 days in the surgical group to avoid unblinding. The blinded outcome assessor will perform dynamometric measurements at baseline, six weeks, 3 months, 6 months, 9 months and 18 months. The MicroFet 2 dynamometer, distributed by ProCare, will be used in all participating centers.

#### **8.7.5 Six-minute walk test (6MWT)**

**The primary endpoint is the difference in distance covered in meters during the six-minute walk test (6MWD) between baseline and 9 months after randomization.** The distance in meters covered during the six-minute walk test at 6 weeks, 3 months, 6 months and 18 months will be recorded as secondary endpoint. Including a six-minute walk test at earlier time points will allow us to assess the 6MWD before any possible cross-over could have occurred. Moreover, a quicker improvement in gait as measured by the 6MWT may also represent an important outcome parameter. Each assessment will be performed by the outcome assessor. Performing the six-minute walk test is not considered standard of care.

Based on a literature analysis and patient feedback on the trial design, gait analysis and recovery of a normal gait pattern are crucial in the recovery of foot drop. In 88% of interviewed patients, success of treatment was related to improvement in gait. The distance covered during the six-minute walk test (6MWD) is validated and clinically used in gait analysis. Several advantages exist in daily practice when using the 6MWT. There is no need for expensive equipment and the test can be performed in every hospital. It is possible to work in a very standardized manner and patient instructions can be easily understood. Since we measure speed and distance over a period of 6 minutes, we get much more information about gait than during a shorter version of the test. It is also possible to detect fatigability. Since we look at differences between baseline values and values after 9 months, the influence of comorbidities (such as age, pulmonary or cardiac problems, ...) can be limited.

The 6MWT has been used in other studies examining foot drop due to other pathologies including multiple sclerosis and stroke (32-34, 82-85). Baseline values for these pathologies are therefore available. Unfortunately, direct baseline values from previous trials of patients with foot drop due to peroneal nerve entrapment are non-existent. Moreover, the data available from other trials concerning foot drop due to different pathology are expected to differ from the foot drop trial study population because of the following reasons:

- The available data on foot drop are extracted from a population with either multiple sclerosis or ischemic stroke. These neurological conditions differ greatly from a peripheral, focal neuropathy. In these patients, the neurologic deficits are caused by lesions in the brain resulting in other clinical presentations which are more generalized compared to an isolated foot drop. Our trial will be able to provide better quantitative measures related to foot drop in this patient population. Currently we only have qualitative evidence based on interviews that walking is hampered in patients with foot drop due to peroneal nerve entrapment.
- Based on our review of the literature, we expect large numbers of patients to recover partially or fully after peroneal nerve entrapment, regardless of the treatment modality. Good outcome after surgical treatment varied between 41% and 100% and good outcome after conservative treatment varied between 53% and 100% (see Section 1 and 2). This rate of recovery is different from recovery in patients with multiple sclerosis or stroke.
- Extrapolation of data is further complicated when MS or stroke patients are allowed to use a foot-ankle orthosis during the 6MWT.

Since the 6MWT is a widely used test, reference data about distance covered in the normal population are available (59, 60, 66-71). We can only provide data on healthy subjects which can serve as surrogate

markers for the optimal outcome for patients. As mentioned before (see Section 8.7.1: time to recovery), the reference equation of Gibbons et al. (60) will be used to predict the normal 6MWD for each subject. Minimal normal 6MWD is defined as 82% of the predicted 6MWD (59). Information on the minimal clinically important difference (MCID) in 6MWD is important to assess the clinical relevance of the primary endpoint. These data are available from previous cited trials, including patients with foot drop due to central pathology (stroke, MS).

- The minimal clinically important difference was estimated at 50 meters in the study of Sankaranayan et al. (82).
- McLoughlin (83) estimated that a clinically meaningful increase in 6MWD by MS-patients is 100 meters (n=40). This number is based on the difference in 6MWD in patients with mild and moderate MS (defined using the Expanded Disability Status Scale (EDSS)) in Goldman's paper (86).
- Fulk (84) estimated the minimal important difference in 6MWD for stroke patients 2 months post-stroke. Fulk performed a secondary analysis of the data of the LEAPS rehabilitation trial (n=265)(87). Two anchors of important change were used: the modified Rankin Scale (mRS) and the Stroke Impact Scale (SIS). The estimated MCID of the 6MWD was 71 meters with the mRS as the anchor and 65 meters with the SIS as the anchor. For participants with initial gait speed (IGS) <0.40 m/s, the estimated MCID was 44 meters with the mRS as the anchor and 34 meters with the SIS as the anchor. For participants with IGS ≥0.40 m/s, the estimated MCID was 71 meters with the mRS as the anchor and 130 meters with the SIS as the anchor.
- In another publication, Fulk (85) determined the minimal detectable change (MDC90) in rehabilitating stroke patients (n=37) defined as the amount of change that must be observed before the change can be considered to exceed the measurement error and variability at the 90% confidence level. For people who could walk without physical assistance, the MDC90 was 61 meters and for people requiring physical assistance, the MDC90 was 39 meters. Overall MDC90 was 54.1 meters.

The 6MWT is widely used to assess functional exercise capacity in cardiovascular and respiratory pathology (88). Bohannon (89) published a systematic review of reported MCID on the 6MWD in adults with pathology. They concluded that a change of 14.0 to 30.5 meters may be clinically important across multiple patient groups.

Based on the available data in the stroke and MS literature, the reference values in a normal population and the work of Bohannon, **we estimate the minimal clinically important difference in 6MWD in patients with foot drop due to peroneal nerve entrapment to be 10% of the minimal predicted age- and sex-specific reference value for that patient (see Appendix 5)**. This value corresponds to a certain level with the range of MCID documented in stroke pathology. The MCID will be taken into account to determine relevance of the difference in 6MWD between the two patient groups. An example:

Suppose the baseline mean 6MWD is 300 meters in the conservative arm and surgical arm of the trial (no difference due to randomization). Mean difference in 6MWD in the surgical arm between baseline and 9 months is 120 meters and mean difference in 6MWD in the conservative arm between baseline and 9 months is 100 meters. Therefore, the difference between both groups is 20 meters. Apart from the assessment of statistical significance, the clinically relevant difference will be defined as the minimum of 10% of the mean minimal predicted age- and sex specific reference value of all patients in the conservative and surgical arm. E.g. assuming an average age of 55 years and 42% of the patients being female(3), the minimal mean predicted 6MWD would be 551.86 meters, resulting in a MCID of 55.2 meters. The actual value applied will be determined by the trial population.

Standardized 6MWT methodology is essential for reproducible and reliable results. The test should be performed in a minimally trafficked area along a flat, straight corridor ideally ≥ 30 meters in length (90, 91). Although the procedural guidelines, formulated in 2002, were made to address patients with respiratory pathology, several items can make the 6MWT in the foot drop trial more standardized:

1. Mark the starting line with brightly colored tape.
2. Mark the length of the hallway every 3m.
3. Mark turn around with a cone.

4. Patients should be wearing comfortable clothing and use their usual walking aids. The use of a foot-ankle orthosis is prohibited.
5. The patient should rest for at least 10 min prior to commencement of testing.
6. Patients should not have exercised vigorously within 2 hours of beginning the test.
7. All patients will be instructed to cover as much distance as possible during six minutes.
8. Subjects will be encouraged every minute. The remaining time will be communicated every minute. An example: When the timer shows 3 minutes remaining, tell the patient the following: "You are doing well. You have only 3 minute left."
9. If the patient stops during testing, the timer should not be stopped. The time at which the patient stopped, and recommenced walking should be noted.
10. Walk distance is measured by counting the number of full laps and rounding to the nearest meter for the partial final lap.

The 6MWD will be evaluated twice at each visit (as first and last assessment), taking the 'learning effect' into account. Furthermore, the applied reference values are based on repeated 6MWD. Best 6MWD will be documented in the eCRF.

#### ***8.7.6 Ability to walk barefoot***

Outcome based on patient interview/experience (yes / no). The ability to walk barefoot will be noted by the outcome assessor using the list of standard assessments at baseline, six weeks, 3 months, 6 months, 9 months and 18 months after randomization.

#### ***8.7.7 Stanmore Questionnaire***

Through the Stanmore questionnaire, functional outcome can be assessed. The Stanmore questionnaire has been used in the literature to assess functional outcome in patients with foot drop due to peroneal nerve injury (94-96). Seven sections (pain, need for orthosis, normal shoes, functional outcome, muscle power, degree of active dorsiflexion and foot posture) add up to a sum score of 100 points. All cited studies used the same classification system for excellent, good, fair and poor:

- Excellent outcome: 85 to 100 points
- Good outcome: 70 to 84 points
- Fair outcome: 55 to 69 points
- Poor outcome: < 55 points

Gait assessment through the Stanmore Questionnaire is not considered standard of care. The Stanmore Questionnaire will be assessed by the outcome assessor at randomization, 6 weeks, 3 months, 6 months, 9 months and 18 months after randomization.

Categories	Points
Pain (15 points)	
No pain at any time or not worse	15
Mild pain or slightly worse	10
Moderate pain or moderately worse	5
Severe pain or markedly worse	0
Need for orthosis (15 points)	
No	15
Occasional (once a week)	10
Frequently (twice a week)	5
Regularly (greater than twice a week)	0
Normal shoes (5 points)	
Yes	5
Yes, but prefers certain types	3
No	0
Functional outcome (10 points)	
Normal daily activity and normal recreation	10
Normal daily activity and limited recreation	6
Limited daily activity and recreation	3
Severe limitation on daily activity and recreation	0
Muscle power (modified Medical Research Council grading) (25 points)	
Grade 4+ or 5	25
Grade 4	20
Grade 3	10
Grade 2 or less	0
Degree of Active Dorsiflexion (degrees) (25 points)	
Greater than 6	25
0-5	20
-5 to -1	10
-10 to -6	5
less than -11	0
Foot posture (5 points)	
Plantigrade, balanced, no deformity	5
Plantigrade, mild deformity	3
Obvious deformity or malalignment	0
Total	100

The Stanmore questionnaire, as used in Yeap et al.(96)

### 8.7.8 Need for ankle-foot orthosis

The need for ankle-foot orthosis will be scored as part of the Stanmore questionnaire, but will be recorded separately as well (baseline, 6 weeks, 3 months, 6 months, 9 months and 18 months). The outcome assessor will document the need for an ankle-foot orthosis at each visit in the list of standard assessments and the eCRF.

### 8.7.9 Gait speed in the 10-meter walk test

Walking speed is an important aspect of gait and is often used as an objective measure of functional mobility. The 10-meter walk test is a commonly used and validated tool to assess gait speed.

[figure not shown]
To our knowledge, gait speed during the 10-meter walk test has not been mentioned in the assessment of foot drop due to peroneal nerve entrapment in the available literature. However, the test is used to assess gait speed in stroke literature (32, 82, 97) since gait velocity is a powerful indicator of function and prognosis after stroke (97) and the most efficient in predicting ambulation classification (98). In stroke literature, gait velocity is often interpreted in the context of community ambulation, broadly defined as locomotion outdoors to encompass activities such as visits to the supermarket, shopping mall and bank, social outings, vacations and pursuit of leisure activities (98, 99). Extrapolation of these data to patients with foot drop due to peroneal nerve entrapment needs to be done with caution, for the same reasons as mentioned in the discussing of the six-minute walk test. Lord (99) defined 4 'community ambulation groups' in a sample of 130 post-stroke patients. Only patients discharged to a private home were included, which means that outcome after stroke was rather good. This improves the resemblance to patients with foot drop due to peroneal nerve entrapment.

- Community ambulation group 1 (not ambulant outside their home): 0.52 m/s (mean)
- Community ambulation group 2 (ambulant as far as the letterbox): 0.66 m/s (mean)
- Community ambulation group 3 (ambulant in the immediate environment): 0.82 m/s (mean)
- Community ambulation group 4 (ambulant in a shopping center and/or places of special interest): 1.14 m/s (mean)

Apart from the data from the stroke literature, reference values are available in the literature (100). Samson (101) defined reference values in a Dutch patient sample based on age and sex (see Appendix 6). Bohannon reported the MCID for change in comfortable gait speed measurements in patients with pathology in his systematic review (102). He concluded that changes in gait speed of 0.10 to 0.20 m/s may be important across multiple patient groups. Sankaranarayanan estimated the MCID in gait speed in stroke patients to be 0.16 m/s (82).

Based on these data, **good outcome in terms of gait speed (m/s), as measured by the 10-meter walk test, is defined as gait speed  $\geq 1.14$  m/s. The MCID for gait speed in patients with foot drop due to peroneal nerve entrapment is estimated to be 0.15 m/s.**

In the 10-meter walk test, patients are instructed to walk at their usual, comfortable pace. Time is measured after a 5 meter stroke for acceleration (at the end there is a 5 meter stroke for deceleration (103). Determining gait speed through the 10-meter walk test is not considered standard of care. The 10-meter walk test will be carried out by the outcome assessor as baseline assessment, at 6 weeks, 3 months, 6 months, 9 months and 18 months after randomization.

**Figure 2.** Set-up of the 10-meter walk test as described by Peters et al.(104).

Determining gait speed with the 10-meter walk test is not considered standard of care.

### 8.7.10 Sensory Changes

In a large retrospective patient series on peroneal nerve decompression after weight loss, Broekx et al. (2018) examined the recovery of sensory deficits (64). Symptoms qualified as sensory included the presence of hypoesthesia and/or paresthesia. They used the following system to assess sensory symptoms:

- Complete recovery: the absence of any sensory symptoms
- Partial recovery: patients with a minimum of sensory symptoms
- No recovery: patients with no improvement

The same system will be used to assess and compare the evolution of sensory symptoms in the foot drop trial. Sensory changes will be evaluated at baseline and at the visits at 6 weeks, 3 months, 6 months, 9 months and 18 months after randomization by the outcome assessor. Sensory changes at 10 days will be assessed by the treating physician. Documenting sensory function is considered standard of care.

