## 7 ELIGIBILITY CRITERIA

### 7.1 Inclusion criteria

For inclusion in the study, the subject must fulfil the following inclusion criteria:

- Written informed consent to participate in the study must be obtained from the subject or proxy / legal representative prior to initiation of any study-mandated procedure
- EDX-documented peroneal nerve entrapment with persisting ( $10 \pm 4$  weeks) foot drop (MRC-score  $\leq 3$ )
- Imaging (ultrasound/MRI) performed to exclude a compressive mass
- Age  $\geq 18$  years

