#### **8.7.13 Surgical Complications**

Overall, neurolysis of the peroneal nerve is considered a low-risk surgery (113). Surgical complications will be assessed by the treating physician at 10 days and 6 weeks. This is considered standard of care. We will use a list of possible complications based on the available literature (1, 3, 43, 44, 47, 48, 50, 51, 55) and our own experience. In this way, surgical complications can be uniformly scored throughout all participating centers. Unforeseen complications will be recorded as free-text. After cross-over, surgical complications will be assessed by the outcome assessor at the extended follow-up visit (18 months).

List of predefined possible surgical complications:

Impaired/prolonged wound healing
Wound infection with need for antibiotics
Wound dehiscence without need for revision surgery
Wound dehiscence with need for revision surgery
Postoperative hematoma without need for revision surgery
Postoperative hematoma with need for revision surgery
(partial) Transection of peroneal nerve with new sensory deficit
(partial) Transection of peroneal nerve with new motor deficit
Persisting pain in the operated area
Development of complex regional pain syndrome

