### SENSORY FUNCTION

Symptoms qualified as sensory included the presence of hypoesthesia and/or paresthesia. Please use following system to assess sensory symptoms (compare to the contralateral healthy side):

- Complete recovery: the absence of any sensory symptoms
- Partial recovery: patients with a minimum of sensory symptoms
- No recovery: patients with no improvement

.....	.....	recovery
-------	-------	----------

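### The sensory scale records recovery only: it cannot separate worsening from no change in patients symptomatic at baseline, and it labels some patients who never had symptoms as recovered

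*Protocol*

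**What the plan says.** Section 8.7.10 takes a three-level system from a retrospective series of operated patients and adopts it unchanged: "The same system will be used to assess and compare the evolution of sensory symptoms in the foot drop trial". The levels are "Complete recovery: the absence of any sensory symptoms"; "Partial recovery: patients with a minimum of sensory symptoms"; and "No recovery: patients with no improvement". Sensory symptoms mean hypoesthesia and/or paresthesia.

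The scale is not confined to follow-up: "Sensory changes will be evaluated at baseline and at the visits at 6 weeks", with further ratings to 18 months. The treating physician adds a 10-day rating in the surgical arm. The table in section 8.8 also shows sensory ratings at screening and randomisation.

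Appendix 4, the data form, repeats the three levels and instructs: "Please use following system to assess sensory symptoms (compare to the contralateral healthy side". It offers no option for never affected, new or worse.

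Section 4.3.2 places sensory changes under complications and neurological deficits. Section 2 says that complications of both treatments, sensory changes among them, will be recorded. Section 7.1 requires "EDX-documented peroneal nerve entrapment with persisting" foot drop with an MRC score of 3 or less, imaging, age and consent. It does not require any sensory symptom.

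**The concern.** A scale built to describe how existing deficits resolved after surgery is being used for two further purposes: describing baseline status, before any recovery is possible, and detecting sensory harm in both arms. Its levels mix two frames of reference. The upper two describe the current state, while the lowest describes change from an earlier state. The form adds a third by asking for comparison with the healthy side.

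At stake is a structured, blinded, two-arm record of whether sensation got worse, in a trial where one arm has surgery on the nerve. If the form does not collect that distinction at the visit, no later analysis can restore it.

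**Working it through.** The protocol states no figure for this outcome, so there is nothing to reproduce. The check applies the definitions literally.

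**Inputs.** The three level definitions (8.7.10, Appendix 4), the visit schedule (8.7.10, 8.8) and eligibility (7.1). For the check, true symptom severity is set at four states: none, minimal, moderate, severe. *No improvement* is read as follow-up severity at or above baseline, with some symptoms present.

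**Step 1: all 16 baseline-by-follow-up patterns.**

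| Baseline | Follow-up | True course | Level(s) met |
|---|---|---|---|
| none | none | never affected | complete |
| none | minimal | new | partial, and also no recovery |
| none | moderate or severe | new | no recovery |
| minimal, moderate or severe | none | resolved | complete |
| minimal | minimal | unchanged | partial, and also no recovery |
| minimal | moderate or severe | worse | no recovery |
| moderate or severe | minimal | improved | partial |
| moderate | moderate | unchanged | no recovery |
| severe | severe | unchanged | no recovery |
| moderate | severe | worse | no recovery |
| severe | moderate | improved | none fits |

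**Step 2: patients symptomatic at baseline.** The three worsening patterns (minimal to moderate, minimal to severe, moderate to severe) all receive *no recovery*. The three unchanged patterns (minimal, moderate, severe) also qualify for it. For moderate or severe symptoms at baseline the codes are identical. For minimal symptoms at baseline a shift from *partial* to *no recovery* might suggest worsening, but unchanged minimal symptoms meet both definitions, so the shift is not reliable evidence. Severe symptoms that become moderate fit no level.

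**Step 3: patients symptom-free at baseline.** Eligibility allows them. Staying normal is coded *complete recovery*. New minimal symptoms satisfy *partial recovery*, so a new deficit can be filed as a recovery. New marked symptoms are coded *no recovery*. New symptoms can be recognised only by setting the follow-up code against the baseline code.

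**Step 4: other capture.**
- The predefined complication list (8.7.13) mentions a new sensory deficit only as "partial) Transection of peroneal nerve with new sensory deficit". It applies to operated patients, at 10 days and 6 weeks and, after cross-over, at 18 months. Free text is allowed.
- Adverse events (10.2) depend on patients reporting events related to the intervention.
- Electrodiagnostics (8.7.2) include a superficial peroneal sensory potential in both arms, at screening and again at 3 and 9 months. This measures conduction, not symptoms.

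**Step 5: illustration only.** Let *a* be the share symptom-free at baseline and *r* the true complete-recovery rate among the rest. Both are assumptions. If every randomised patient were counted, the apparent rate would be a + (1 − a)r.
- With r = 50%: a = 10% gives 0.10 + 0.90 × 0.50 = 55%; a = 40% gives 0.40 + 0.60 × 0.50 = 70%.
- A true difference of 20 points (50% against 70%) becomes (1 − a) × 20, which is 18 points at a = 10% and 12 points at a = 40%.

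The protocol does not say that recovery will be computed over all patients, so these figures show what one possible analysis would do, not what is planned.

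**The case against.** Three stronger readings are tempting, and the protocol supports none of them.

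*The scale cannot show any worsening.* This goes too far. Ratings are repeated from baseline, so a patient recorded as symptom-free who later has symptoms changes code. The masking is confined to patients already symptomatic.

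*Reported recovery will be overstated and the treatment difference diluted.* This assumes an all-patients denominator. Section 11.4.4 leaves the analysis of the other secondary endpoints to the SAP, which could exclude patients rated symptom-free at baseline without new data. Even under an all-patients denominator, randomisation balances such patients on average, so neither arm would be favoured.

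*Sensory harm goes unrecorded in the trial.* It does not go wholly unrecorded. Free-text complications, adverse events (section 10.1 counts clinically significant worsening of a pre-existing condition) and the sensory potential each catch something. The Stanmore pain item has grades for worse, and EQ-5D-5L covers pain or discomfort, though neither measures hypoesthesia.

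It can also be said that the scale was borrowed for comparability with a 200-patient series, and that this is one item among the other secondary outcomes in a trial powered only for its primary endpoint. Both points are fair and limit the weight of the finding. They do not remove it. A SAP can choose a denominator, but it cannot tell worse from unchanged, or place the improved-but-not-minimal patient, when the form never asked.

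**Conclusion.** The point holds as a defect in the endpoint definition and the data form. In patients symptomatic at baseline, worsening is not separated from no change, and partial improvement that stays above minimal has no level. In patients without baseline symptoms the labels are wrong: *complete recovery* for a stable normal state and possibly *partial recovery* for a new minimal deficit. New deficits in these patients have to be inferred from the baseline rating. The other sources give partial, unstructured or non-symptom capture.

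The conclusion rests on reading the level definitions literally and on eligibility not requiring sensory symptoms. Its size cannot be stated, because the protocol gives neither the share of patients with sensory symptoms at baseline nor an expected rate of worsening. The primary endpoint, the key secondary endpoint and the sample size are untouched.

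**What to change.** In section 8.7.10 and Appendix 4:

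1. At baseline, record sensory symptoms as none, minimal or more than minimal, and drop the recovery wording at that visit.
2. At each follow-up visit, record the same three levels plus change from baseline: improved, unchanged, or new or worse. State that change is judged against the patient's own baseline, with the healthy side as the reference for what is normal.
3. Report recovery among patients symptomatic at baseline, and new or worse symptoms in all patients by randomised arm as a harm outcome.

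Keeping the minimal level preserves comparability with the source series, because its three levels can still be derived from the new items. The cost is two or three tick-boxes on an assessment already made at every visit, with a small eCRF, protocol and training change across all sites. For visits already completed on the present form, the missing distinction cannot be recovered, so the change is worth making early.
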